9.5. Blinding and code-breaking

Participant, Care Provider, Outcomes Assessor are blinded to the allocation.

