3. SYNOPSIS

Trial Title	Compassion and Metacognition Based Therapy for Schizotypal Personality Disorder: A Pilot Non-inferiority Randomized Controlled Trial on Repeated Measures.
Internal ref. no. (or short title)	Compassion and Metacognition in Schizotypal Personality (CMBT).
Trial registration	Unique Protocol ID: 03-07072020
Sponsor	Tages Onlus [name]
Funder	N/A
Clinical Phase	Recruiting
Trial Design	Parallel Assignment Randomized Controlled Trial with Repeated Measures
Trial Participants	Minimum Age: 18 Years Being diagnosed with Schizotypal Personality Disorder at SCID-5-AMPD
Sample Size	14
Planned Trial Period	Total lenght: December 15, 2020 - December 20, 2021

	Pre-post evaluation between pre-assessment (1-month before the intervention) and 1 month follow-up.		
Planned Recruitment period	December 15, 2020 - September 30, 2021		
	Objectives	Outcome Measures	Timepoint(s)
Primary		Personality pathology: Total score at PID-5-BF	(i) at 1 month before intervention starts; (ii) once the treatment starts; (iii) 6 measurements at the end of each month of intervention; at 1-month follow-up.
Secondary		Schizotypal Personality Disorder Diagnosis: Diagnosis at the 3rd module of SCID-5-PD interview; General Psychopathology: Total score at SCL-90-R; Metacognition: Total score at MAS-A	Pre-post evaluation between pre-assessment (1-month before the intervention) and 1-month follow-up assessment.
Intervention(s)	
 IMP(s) nIMP(s) Other intervention(s) 	Compassion and Metacognition Based Therapy (CMBT): Third Wave Cognitive Therapy targeting metacognitive dysfunctions (through Metacognitively Oriented Psychotherapy) and selfcriticism (through Compassion Focused Therapy). 6-month therapy, including 24 weekly sessions.	
Comparator	Cognitive Behavioral Therapy: Standard Cognitive Behavioral Therapy for Personality Disorders plus Standard Psychopharmacological Treatment. 6-month therapy, including 24 weekly sessions.		

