7. TRIAL DESIGN

Randomized Controlled Trial with Repeated Measures.

After being informed about the study and potential risks, all patients giving written informed consent will undergo a psychological assessment so as to determine eligibility for study entry. Patients who meet the eligibility requirements will be randomized in a double-blind manner in a 1:1 ratio to new integrative

psychotherapy or treatment as usual (cognitive behavioral therapy plus standard psychopharmacological treatment). One month after the conclusion of the two forms of treatment (both lasting 6 months), patients will have access to the final follow-up assessment.

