9. TRIAL PROCEDURES

9.1. Recruitment

The recruitment centers were selected on the basis of their expertise in treating personality disorders and the presence of a multidisciplinary team. Subjects who during epidemiological studies or clinical assessment procedures report a diagnosis of SPD are approached and asked for their willingness to receive a subsequent assessment for possible entry into the study. Once the informed consent has been read and signed, the inclusion and exclusion criteria for the participants are confirmed. Finally, eligible subjects are randomized through software and assigned to treatment.

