10. TRIAL INTERVENTIONS

10.1. Interventions' Description

Cognitive Behavioral Therapy Standard Cognitive Behavioral Therapy for Personality Disorders. Compassion and Metacognition Based Therapy: the intervention is a Third Wave Cognitive Therapy targeting metacognitive dysfunctions (through Metacognitively Oriented Psychotherapy) and selfcriticism (through Compassion Focused Therapy).

Both treatments last 6 months.

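### Section 9.5 lists the care provider as blinded, which a therapist delivering one of two different psychotherapies cannot be; participant blinding is claimed without a described procedure

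*Combined protocol and SAP*

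**What the plan says.** Section 9.5 is a single sentence: "Participant, Care Provider, Outcomes Assessor are blinded to the allocation". Section 7 says that eligible patients "will be randomized in a double-blind manner in a 1:1 ratio". The only mechanism described is in section 9.4, where a CRO prepares the schedule and keeps the allocation from the investigators. Section 9.1 closes with "Finally, eligible subjects are randomized through software and assigned to treatment".

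Section 10.1 describes the experimental arm as a third-wave therapy built on metacognitively oriented psychotherapy and compassion focused therapy. It describes the comparator as "Cognitive Behavioral Therapy Standard Cognitive Behavioral Therapy for Personality Disorders". The synopsis gives the same contact schedule for each arm, "6-month therapy, including 24 weekly sessions", but describes the comparator as "Standard Cognitive Behavioral Therapy for Personality Disorders plus Standard Psychopharmacological Treatment". Sections 6 and 7 also attach medication to the comparator. Section 8.3 excludes anyone already receiving psychotherapy or psychopharmacological treatment.

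**The concern.** A blinding statement tells the reader who could not have been influenced by knowing the treatment. Section 9.5 makes that claim for three roles. For the person delivering the therapy it contradicts the nature of the interventions. For the participant it has no procedure behind it.

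What is at stake is how the primary comparison, the PID-5-BF total score between arms, is described and read. Section 12.1 commits the trial to CONSORT reporting, and section 18 promises lasting access to individual data, so an inaccurate blinding description would travel with the results. A reader would believe that therapist knowledge of the arm had been controlled when it had not, and would believe the same of participants without evidence.

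**Working it through.** The point rests on setting sections side by side, not on a figure. The three roles in section 9.5 are taken in turn.

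**Care provider.**
1. Sections 3 and 10.1: the arms are different therapies with different targets and methods.
2. Section 9.1: each randomised subject is assigned to one of them.
3. To deliver the assigned therapy, the therapist must know which it is. Here the allocation is the choice of therapy, so knowing the therapy is knowing the allocation.
4. Section 9.4: holding the schedule at the CRO can stop an investigator from foreseeing the next assignment. It cannot keep a therapist unaware of the therapy being given.

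The statement therefore fails for this role.

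**Participant.**
1. No section of the text reviewed says how participants would be kept unaware of their arm. The consent form was not part of that text, so a procedure described there cannot be excluded.
2. Section 8.3 requires entry without psychopharmacological treatment. The synopsis and sections 6 and 7 then list medication in the comparator only. On that description, being given medication would tend to reveal the arm.
3. Section 10.1 describes the comparator without medication. On that description, step 2 falls away. The sections conflict, and this review does not say which is right.
4. Section 12.1 provides for patients who refuse the treatment-as-usual arm. This suggests that they know their arm, but does not prove it.

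The claim is therefore unsupported as written, but not shown to be false.

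**Outcomes assessor.** Blinding is feasible if the assessor is kept separate from treatment and allocation. No procedure is given, but nothing in the text contradicts the claim.

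**Effect on the sample size.** The calculation in section 12.2 has no blinding input. With f = 0.37, 2 groups, 9 measurements, correlation 0.50 and N = 12:

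- λ = f² × N × m / (1 − ρ) = 0.1369 × 12 × 9 / 0.50 = 29.57
- df = (2 − 1)(9 − 1) = 8 and (12 − 2)(9 − 1) = 80
- critical F = 2.05637 and power = 0.97857, as the plan states. The plan gives no alpha; 0.05 is inferred because it returns the stated critical F.
- 12 / (1 − 0.10) = 13.3, rounded up to 14, the sample size in the synopsis

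Correcting the blinding description changes none of these figures.

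**The case against.** The strongest reply is that section 7 may mean allocation concealment. Its phrase attaches to the act of randomising, and neither the trial title nor the design row of the synopsis uses the term. That is a fair reading of section 7. It does not rescue section 9.5, which comes after the concealment arrangement in 9.4 and makes its own claim for three named roles.

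A second reply is that *double-blind* is never defined, so participant and assessor could be the two blinded parties. This stands. An unblinded therapist defeats the words *Care Provider* in 9.5, but does not by itself defeat the phrase in section 7. A reader might infer that the primary result cannot be called double-blind at all. The documents do not support that while participant masking remains open.

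A third reply is that the participant argument is one from absence. This also stands in part. The consent form was not reviewed, both arms have the same number and spacing of sessions, and the medication hint depends on sections that disagree. A reader might infer that participants are unblinded, but the text shows only that the claim lacks a described procedure.

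Finally, *Care Provider* might mean someone other than the therapist. The protocol gives no such definition. If that was intended, 9.5 would still need to say so.

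**Conclusion.** The concern holds for the care provider without qualification: section 9.5 states a design property that this trial cannot have. For the participant it holds conditionally: the claim needs a described procedure or should be withdrawn. The assessor claim is left standing.

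No numerical size is attached. A reader might go on to infer that the PID-5-BF result is biased by expectation, for example because it is a self-rating. The documents do not say who completes the instrument, and they give nothing from which the size or direction of any bias could be derived, so that step is not taken. Multiplying participants by sessions would only restate that therapists know what they deliver.

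The conclusion assumes that *Care Provider* includes the treating therapist and that *allocation* means the therapy assigned. It does not depend on which description of the comparator is right. This should be corrected: it concerns how the primary comparison is described, and the correction costs little.

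**What to change.** - **Section 9.5, therapist:** remove *Care Provider* and state that treating therapists are not blinded.
- **Section 9.5, participant, and section 7:** keep *Participant* and *double-blind* only if a participant masking procedure exists, and describe it in 9.5. If none exists, remove both and report the trial as having unblinded therapists and participants.
- **Section 9.5, assessor:** claim blinded outcome assessment only for assessments made by someone kept unaware of allocation.
- **Comparator:** reconcile section 10.1 with the synopsis and sections 6 and 7 on whether medication is part of the comparator, since any account of participant masking depends on it.
- **Reporting:** present the primary comparison under the corrected blinding status.

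The cost is a few lines of text and a less favourable design description. Sample size, measurement schedule, outcome measures and analysis are unchanged. If a participant masking procedure already exists, the only cost on that point is describing it.

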9.6. Early Discontinuation/Withdrawal of Participants

During the course of the trial a participant may choose to withdraw early from the trial treatment at any time. This may happen for a number of reasons, including but not limited to:

- The occurrence of what the participant perceives as an intolerable AE.
- Inability to comply with trial procedures
- Participant decision

Participants may choose to stop treatment and/or study assessments but may remain on study follow-up.

Participants may also withdraw their consent, meaning that they wish to withdraw from the study completely. Participants can withdraw completely from the study and withdraw the data and samples collected up until the point of withdrawal. The data and samples already collected would not be used in the final study analysis. (Any limits to this type of withdrawal where, for example analysis of their data or samples has already been integrated into interim results or dose escalation decisions etc. should be explained in the participant information sheet).

9.7. Definition of End of Trial

The end of trial is the point at which all the data has been entered and queries resolved.

10. TRIAL INTERVENTIONS

10.1. Interventions' Description

Cognitive Behavioral Therapy Standard Cognitive Behavioral Therapy for Personality Disorders. Compassion and Metacognition Based Therapy: the intervention is a Third Wave Cognitive Therapy targeting metacognitive dysfunctions (through Metacognitively Oriented Psychotherapy) and selfcriticism (through Compassion Focused Therapy).

Both treatments last 6 months.

11. SAFETY REPORTING

11.1. Adverse Event Definitions

Adverse Event (AE)	Any untoward medical occurrence in a participant to whom the intervention has been administered, including occurrences which are not necessarily caused by or related to that treatment.
Serious Adverse Event (SAE)	
A serious adverse event is any untoward medical occurrence that:
 
• results in death• is life-threatening• requires inpatient hospitalisation or prolongation of existing hospitalisation• results in persistent or significant disability/incapacity• consists of a congenital anomaly or birth defect*. 
Other 'important medical events' may also be considered a serious adverse event when, based upon appropriate medical judgement, the event may jeopardise the participant and may require medical or surgical intervention to prevent one of the outcomes listed above.
 
NOTE: The term "life-threatening" in the definition of "serious" refers to an event in which the participant was at risk of death at the time of the event; it does not refer to an event which hypothetically might have caused death if it were more severe.

12. STATISTICS

12.1. Statistical Analysis Plan (SAP)

Primary outcomes will be evaluated through repeated measures ANOVA. Statistical analyses and reporting will be conducted following CONSORT guidelines, with the primary analyses based on the ITT principle, which considered data from all participants whose baseline data were available. Multiple imputation will be adopted to estimate mid-assessment, post-treatment, and follow-up scores for noncompleters (e.g., those who had missed plus than 10% of sessions, or those who decline to participate in the TAU condition). Additionally, we will also conduct per-protocol (PP) analyses, which refers to inclusion in the analysis of only those patients who strictly adhered to the protocol.

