6. OBJECTIVES AND OUTCOME MEASURES

Objectives	Outcome Measures	Timepoint(s) of evaluation of this outcome measure (if applicable)
Primary Objective To compare the effect of the CMBT-S versus CBT plus standard psychopharmacotherapy for SPD.	
 Change in Personality pathology: Total score at PID-5-BF Schizotypal Personality Disorder Diagnosis: Diagnosis at the 3rd module of SCID-5-PD interview; General Psychopathology: Total score at SCL-90-R; Metacognition: Total score at MAS-A 	9 measurements: (i) at 1 month before intervention starts; (ii) once the treatment starts; (iii) 6 measurements at the end of each month of intervention; at 1-month follow-up; Pre-post evaluation between pre-assessment (1-month before the intervention) and 1-month follow-up assessment.
Secondary Objectives To assess the safety of CMBT-S in patients diagnosed with SPD	
 Dropout rate Completion rate Adverse events (suicidal behaviors, self-harm, psychotic episodes) rate 	At the end of the intervention: dropout rate ($\leq 10\%$ of subjects), completion rate ($\leq 10\%$ of sessions skipped), adverse event rate ($\leq 10\%$ of subjects).

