12.2. Sample Size Determination

ANOVA: Repeated measures, within-between interaction has been conducted in order to a priori compute required sample size. As input we estimate ([name], 2020) an effect size f equal to 0.37 with a power $(1-\beta)$ equal to 0.95. Moreover, we considered 9 measurements with at least a correlation among them equal to 0.50 (PID-5-BF reports a test-retest value greater than 0.70). This led to a total sample equal to 12 (critical $F= 2.0563726$; actual power= 0.9785743). By considering at least 10% of withdrawal we

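### Section 12.1 leaves the imputation model open for nine PID-5-BF waves in 14 people; a parsimonious mixed model on all observed scores would be a safer primary analysis

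*Combined protocol and SAP*

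**What the plan says.** The synopsis (section 3) gives "Sample Size 14", and section 7 plans 1:1 allocation, so 7 per arm if the split is exact. Section 6 schedules the PID-5-BF total score as "9 measurements: (i) at 1 month before intervention starts; (ii) once the treatment starts; (iii) 6 measurements at the end of each month of intervention", plus the 1-month follow-up. Section 12.2 uses the same count: "we considered 9 measurements with at least a correlation among them equal to 0.50 (PID-5-BF reports a test-retest value greater than 0.70").

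Section 12.1 makes repeated measures ANOVA the primary analysis, on an ITT set of everyone with baseline data. For missing scores it says "Multiple imputation will be adopted to estimate mid-assessment, post-treatment, and follow-up scores for noncompleters". Non-completers are, by example, people who missed more than 10% of sessions or who declined the comparator condition. A per-protocol analysis is added. The section gives no imputation model, predictor list, number of imputations, pooling rule or fallback.

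**The concern.** Repeated measures ANOVA needs complete rows, so under ITT the primary result depends on the imputation step. Nine waves are many for 14 people. An imputation regression that uses every earlier wave is nearly saturated before anyone leaves, and each leaver removes one of the few residual degrees of freedom.

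Section 12.1 as worded permits an analysis that costs little precision, one that more than doubles the interval, and one that cannot be fitted. The choice would be made after the data are seen or left to software settings. The risk is mainly to precision: in the simulations below the unrestricted imputation intervals were too wide, with coverage near 100%, rather than anti-conservative.

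**Working it through.** **1. The plan's own figure.** Inputs from section 12.2: "an effect size f equal to 0.37 with a power $(1-\beta)$ equal to 0.95", 9 measurements, correlation 0.50. Alpha is not stated; 0.05 is implied by the critical F. For the within-between interaction, noncentrality = f² × N × m / (1 − ρ) = 0.37² × 12 × 9 / 0.5 = 29.57, with df 8 and (12 − 2) × 8 = 80. This gives critical F 2.0564 and power 0.9786, matching "critical $F= 2.0563726$; actual power= 0.9785743". N = 10 gives 0.941, so 12 is the smallest even N that reaches 0.95. Then 12 / 0.9 = 13.3, rounded up to the synopsis figure of 14. The plan thus has room for about two leavers.

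**2. Degrees of freedom, unrestricted imputation model.** Coefficients for wave 9: intercept 1 + arm 1 + earlier waves 8 = 10. Residual df = (14 − leavers) − 10.

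| Leavers | People with wave 9 | Residual df | P(at least this many), binomial, 14 people at 10% |
|---|---|---|---|
| 2 | 12 | 2 | 42% |
| 3 | 11 | 1 | 16% |
| 4 | 10 | 0 | 4% |

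At 0 df the fit is exact, the residual variance cannot be estimated, and proper imputation draws are undefined.

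**3. Cost of two leavers, unrestricted model.** Simulation with 14 people, 20 imputations, Rubin pooling with small-sample df, compound symmetry 0.5 or 0.7, and leavers seen only at the first two waves. Against no missing data, the standard error rises 2.0 to 2.5-fold and the median 95% interval widens 2.2 to 2.8-fold. Against complete cases, the interval is 2.0 to 2.5 times as wide. With three leavers it is about 8 to 12 times as wide as with no missing data.

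**4. Comparison with REML.** Drop-out from month 3; contrast = arm difference in change from treatment start to follow-up; no true difference. Median 95% half-widths in outcome SD, as ranges over simulation runs:

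| Leavers | Correlation assumed | MI, all earlier waves | MI, restricted | REML |
|---|---|---|---|---|
| 2 | compound symmetry 0.5 | 3.0–3.2 | 1.33–1.42 | 1.23–1.24 |
| 2 | AR(1) 0.85 | 2.8–3.0 | 1.55–1.58 | 1.43–1.45 |
| 4 | compound symmetry 0.5 | not estimable | 1.67–1.93 | 1.38 |
| 4 | AR(1) 0.85 | not estimable | 1.86–2.06 | 1.56 |

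Unrestricted MI against REML with two leavers: 3.0 / 1.24 = 2.4 and 2.9 / 1.43 = 2.0. Together with step 3, the range is about 2.0 to 2.8.

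Restricted MI against REML with two leavers, within one set of runs: 1 − 1.23/1.42 = 13% and 1 − 1.45/1.55 = 6% narrower under REML. Over one to four leavers the gap was about 4 to 27% narrower. Put the other way, the restricted MI interval is 1/0.96 − 1 = 4% to 1/0.73 − 1 = 37% wider. With one leaver the gap is small and close to simulation error.

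**5. Complete cases.** At correlation 0.5, half-widths are 1.24 SD (two leavers) and 1.41 SD (four), against REML 1.24 and 1.38. For this contrast REML gains almost no precision over dropping the leavers.

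**6. Who is imputed.** More than 10% of 24 sessions is more than 2.4, so three or more missed. This rule works on attendance, not on missing scores. The documents give no rate of missed sessions. As an assumption, if sessions are missed independently at 5%, about 12% of participants become non-completers, and four or more among 14 has probability 7%. At 8% missed, the figures are 30% and 65%. Read literally, the rule could send more people to imputation than withdrawal alone.

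**The case against.** A reader might infer that multiple imputation is unworkable in this trial, or that the primary analysis cannot be fitted once four people leave. The documents do not support that. Section 12.1 does not say that all earlier waves enter each regression. With few predictors, imputation runs with two or four leavers, at about 1.1 to 1.3-fold and 1.2 to 1.7-fold the no-missing-data interval. Its mention of mid-assessment, post-treatment and follow-up scores could even mean fewer waves. With start, mid and post scores as predictors, the last regression has 5 coefficients, and four leavers still leave 10 − 5 = 5 df. Sections 6 and 12.2 favour nine waves, but the ambiguity is real.

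The comparison in step 4 also rewards parsimony more than likelihood. An unstructured nine-visit covariance has 9 × 10 / 2 = 45 parameters, which 14 people cannot support either. At 10% withdrawal, none or one leaver is the likelier outcome (58%). With one leaver even the unrestricted model gives 1.70 SD against 1.11 SD with no missing data (correlation 0.5).

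All of this stands, and it limits the claim. It does not remove the open choice of model, nor the gap of a few per cent to about a quarter between restricted imputation and a simple mixed model. Complete cases match REML for precision on the final-wave contrast, but they discard leavers and so depart from the ITT set in section 12.1.

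**Conclusion.** The point holds as a cheap improvement that should be made, not as a fatal flaw. Firm, by counting: with all earlier waves and arm as predictors, two leavers leave 2 residual df and four leave 0. Conditional on the assumed model: about 2.0 to 2.8-fold widening with two leavers, and REML about 4 to 27% narrower than restricted imputation.

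The conditional figures rest on assumptions outside the documents: compound symmetry at 0.7 and AR(1) at 0.85 (0.5 is the plan's value), the drop-out time, and a fitted covariance family that suits the data. They concern one contrast, change from treatment start to follow-up, and not the 8-df interaction test; how that test would be pooled over imputations is also unstated. The case for the mixed model is that it keeps every observed score and the ITT set under missing-at-random without an imputation model, not that it gains precision over complete cases.

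**What to change.** In section 12.1:

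- Make the primary analysis a linear mixed model for repeated measures with arm, visit and arm-by-visit, one pre-specified covariance (compound symmetry or AR(1)), REML and small-sample degrees of freedom. Compound symmetry fits the single correlation in section 12.2.
- Fit it to all observed PID-5-BF scores of all randomised participants, and state that observed scores of people who missed sessions are kept.
- Keep multiple imputation only as a sensitivity analysis, with predictors limited to arm, treatment-start score and last observed score, and with the number of imputations and the pooling rule stated.

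The cost is SAP wording; no participants, visits or data are added. The downside is that a covariance structure must be chosen in advance and may be wrong.

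### The imputation rule in section 12.1 does not match the nine scheduled PID-5-BF measurements, so people who stop assessments early may fall out of the ITT analysis

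*Combined protocol and SAP*

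**What the plan says.** Section 6 sets the PID-5-BF schedule as "9 measurements: (i) at 1 month before intervention starts; (ii) once the treatment starts", followed by six end-of-month scores and a follow-up score. The Synopsis (section 3) gives the same later visits: "6 measurements at the end of each month of intervention; at 1-month follow-up". Section 12.2 sizes the trial on that schedule: "we considered 9 measurements with at least a correlation among them equal to 0.50".

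Section 12.1 analyses the primary outcome by repeated measures ANOVA on the ITT principle, counting everyone with baseline data. For missing scores it says: "Multiple imputation will be adopted to estimate mid-assessment, post-treatment, and follow-up scores for noncompleters". Its examples of noncompleters are people who miss more than 10% of sessions or who decline the comparator treatment. Neither example refers to a missing score.

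Section 9.6 allows participants to stop treatment, assessments or both while staying in follow-up.

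**The concern.** The imputation sentence uses visit labels that the schedule does not use, and nothing says which visit is the mid-assessment. The label cannot belong to the SCL-90-R, MAS-A or SCID-5-PD, because sections 3 and 6 give those only a pre-treatment and a follow-up assessment. It must therefore refer to the PID-5-BF, which has six in-treatment scores.

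Classical repeated measures ANOVA needs a value at every wave for each person. If some monthly waves are outside the imputation rule, a person with gaps there is dropped, although the same section promises to keep them. People who stop assessments early may well differ from those who stay, so dropping them can bias the comparison. In a trial of 14, each person is about 7% of the sample (1/14). Two analysts could also follow section 12.1 in good faith and analyse different people.

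**Working it through.** **Step 1. The plan's own figure.** Inputs from section 12.2: f = 0.37, correlation ρ = 0.50, m = 9 measurements, N = 12. Section 7 gives two arms at 1:1, so k = 2. Alpha is not stated; 0.05 is assumed and is confirmed by the critical F. Sphericity is assumed. For the within-between interaction:

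- λ = f² × N × m / (1 − ρ) = 0.1369 × 12 × 9 / 0.50 = 29.57
- df1 = (k − 1)(m − 1) = 8
- df2 = (N − k)(m − 1) = 10 × 8 = 80
- Critical F = 2.0563726 and power = 0.9785743, both exactly as stated.

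Allowing for 10% withdrawal, 12 / 0.90 = 13.3, which rounds up to the 14 in the Synopsis. The sample size calculation is internally correct for nine waves.

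**Step 2. The schedule against the imputation rule**, taking the mid-assessment as one visit at month 3 (an assumption):

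| PID-5-BF measurement | Named for imputation in 12.1? |
|---|---|
| 1 month before treatment | No (pre-treatment) |
| Treatment start | No (pre-treatment) |
| Month 1 | No |
| Month 2 | No |
| Month 3 | Yes, as mid-assessment |
| Month 4 | No |
| Month 5 | No |
| Month 6 | Yes, as post-treatment |
| 1-month follow-up | Yes |

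Seven scores fall after treatment start (6 + 1). Three are named and 7 − 3 = 4 are not.

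**Step 3. Who may be lost.** Someone who stops assessments after month 2 has months 3 and 6 and follow-up imputed, but months 4 and 5 stay empty, and a complete-case nine-wave ANOVA drops them. Someone who stops after month 5 lacks only month 6 and follow-up, both named, and is kept. The exposed group is therefore anyone who lacks a score at month 1, 2, 4 or 5. That includes a person who stops monthly assessments and returns for follow-up, as section 9.6 allows.

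**Step 4. Effect on power.** Same formula, nine waves, 14 enrolled, with losses removed from the total N:

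| Lost | Analysed | Power |
|---|---|---|
| 0 | 14 | 0.993 |
| 1 | 13 | 0.988 |
| 2 | 12 | 0.979 |
| 3 | 11 | 0.964 |
| 4 | 10 | 0.941 |
| 5 | 9 | 0.905 |

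The planned allowance is 10% of 14, or 1.4 people. Power falls below the 0.95 target only from four losses (4/14 = 29%).

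**The case against.** The label may be meant by phase: scores during treatment, at its end, and at follow-up. On that reading all seven later scores are covered and nothing is left empty. Section 12.1 states no rule for deleting incomplete cases; deletion is inferred from how classical repeated measures ANOVA works. Reading a loose label as an instruction to leave four waves blank also sits badly with the ITT commitment in the same section. Nor does leaving treatment by itself mean missing scores, since section 9.6 lets people stay in follow-up. Those who withdraw consent completely have their data removed under section 9.6 and are lost under any imputation rule.

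All of this stands as a limit on the consequence, which is conditional. It does not remove the defect. The plan does not say which reading applies, and on the literal one the imputation rule does not deliver the ITT set that the section promises.

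**Conclusion.** The point holds as an incomplete and unclear imputation rule. Three of the seven scores after treatment start are named if the mid-assessment is a single visit. People who stop assessments before the end of month 5 may then be dropped from the ITT analysis. This assumes that their monthly scores are in fact missing and that the ANOVA is run on complete cases. The harm is an incomplete ITT set and possible bias. The documents do not allow the size of that bias to be estimated.

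Two stronger readings are not supported.

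- **That the trial loses its stated power.** A reader might infer that the ANOVA will use only the named visits. At f = 0.37 and ρ = 0.50, four waves (one pre-treatment score plus three) would give power 0.824 at N = 12 and 0.890 at N = 14. No section proposes such an analysis; sections 3, 6 and 12.2 all rest on nine measurements. The figures also depend on the choices made. Keeping both pre-treatment scores (five waves) gives 0.882 and 0.934. Section 12.2 treats 0.50 as a minimum and notes that "PID-5-BF reports a test-retest value greater than 0.70"; at ρ = 0.70, four waves give 0.969 and 0.988. All of them hold f fixed as waves are removed. For the nine-wave analysis that the plan does specify, power is not materially affected at the planned withdrawal.
- **That the chance of any withdrawal among 14 measures the gap.** A withdrawal becomes a loss through this rule only if a score at month 1, 2, 4 or 5 is missing and the person's data remain usable.

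**What to change.** In section 12.1, replace the three visit labels with: any missing PID-5-BF score at months 1 to 6 and at 1-month follow-up. State that the primary analysis uses all nine scheduled measurements. This also makes a missing score, not missed sessions, the trigger for imputation. Since the nine waves include the treatment-start score, say in the same sentence how a missing value there is handled.

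Alternatively, specify a likelihood-based mixed model on all observed scores, which keeps partial cases without imputing each wave.

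Either change should be fixed before the data are analysed, so that the choice of waves cannot follow the results. The cost is SAP wording and slightly more analysis work. No visits or participants are added, and the sample size in section 12.2 need not change because of this point.
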